## 10 STUDY MANAGEMENT

### 10.1 INVESTIGATOR DELEGATION PROCEDURE

The principal investigator is responsible for making and updating a “delegation of tasks” listing all the involved co-workers and their role in the project. She will ensure that appropriate training relevant to the study is given to all of these staff, and that any new information of relevance to the performance of this study is forwarded to the staff involved.

### 10.2 PROTOCOL ADHERENCE

Investigators ascertain they will apply due diligence to avoid protocol deviations. All significant protocol deviations will be recorded and reported in the Clinical Study Report .

### 10.3 STUDY AMENDMENTS

If it is necessary for the study protocol to be amended, the amendment and/or a new version of the study protocol (Amended Protocol) will be notified to and approved by the The Norwegian Medicines Agency and the REK according to EU and national regulations.

### 10.4 AUDIT AND INSPECTIONS

Authorized representatives of a The Norwegian Medicines Agency and REK may visit the centre to perform inspections, including source data verification. Likewise the representatives from the sponsor may visit the center to perform an audit. The purpose of an audit or inspection is to systematically and independently examine all study-related activities and documents to determine whether these activities were conducted, and data were recorded, analyzed, and accurately reported according to the protocol, Good Clinical Practice, and any applicable regulatory requirements. The principal investigator will ensure that the inspectors and auditors will be provided with access to source data/documents.

## 11 ETHICAL AND REGULATORY REQUIREMENTS

The study will be conducted in accordance with ethical principles that have their origin in the Declaration of Helsinki and are consistent with ICH GCP and applicable regulatory requirements. Registration of patient data will be carried out in accordance with national personal data laws.

### 11.1 ETHICS APPROVAL

The study protocol, including the patient information and informed consent form to be used, has been approved by the Norwegian Regional Ethics Committee South East (REK) at 29 Jun 2017.

### 11.2 OTHER REGULATORY APPROVALS

The study has been approved by the Norwegian Medicines Agency at 15 Jun 2017. The study has been registered in the EU ClinicalTrials Register (EudraCT Number: 2014-003623-21).

### 11.3 INFORMED CONSENT PROCEDURE

The patient information and consent forms are attached in Appendix B. A copy of the patient information and consent will be given to the patients. The signed and dated patient consent forms will be filed in the Investigator Site File binder and also scanned to be part of the patient's electronic medical record at the hospital.

### 11.4 SUBJECT IDENTIFICATION

A paper-based list of all patients (who have received study treatment or undergone any study specific procedure) including a unique code number, patient's initials, date of birth and personal number, full names, addresses, phone-numbers will be established and securely stored at the Dep of Rheumatology, Sykehuset Østfold. In the CRFs the patients will be identified by the corresponding code numbers and initials.

## 12 TRIAL SPONSORSHIP AND FINANCING

The current study is investor-initiated. We will apply for grants from Sykehuset Østfold, Helse Sør Øst and other potential sources for research funding.

## 13 TRIAL INSURANCE

The Principal investigator will have insurance coverage for this study through membership of Legemiddelansvarsforeningen LAF (the Norwegian Drug Liability Association).

## 14 PUBLICATION POLICY

All personnel who have contributed significantly with the planning and performance of the study will be included in the list of authors. Upon study completion and finalization of the study report the results of this study will be submitted for publication in a peer reviewed journal. Final reports will also be submitted to the The Norwegian Medicines Agency (EMA Study Report) and to REK in accordance with national regulations.

Sciatica is an established term for pain along the course of the sciatic nerve, radiating from the lower back or buttock into the leg. Sciatica is also known by terms such as low back-related leg pain, lumbosacral radicular syndrome or radiculopathy. Treatment of sciatica is primarily aimed at pain reduction, either by medication, or surgically by reducing pressure on the nerve root. Given their analgesic and anti-inflammatory mechanisms of action, non-steroidal anti-inflammatory drugs (NSAIDs) have been, and are still being regarded as standard therapy for sciatica. In a survey among American physicians 80% said they would recommend NSAIDs for initial management. In a study from general practice in Italy 90% of the sciatica patients had been prescribed an NSAID. In studies investigating the effect of surgery and manipulation, 50-60% of the patients were taking an NSAID at baseline (see protocol for references). However, the scientific evidence for this practice is generally lacking. Very few randomized controlled trials (RCT) of NSAIDs have been undertaken in patients with sciatica, and no study has shown clinically meaningful effects as compared to placebo.

NSAIDs involve the risk of serious gastrointestinal, vascular and renal side effects. Hence, there is a strong need to clarify their potential beneficial effects in sciatica. Naproxen, the active drug in this study, is a non-selective NSAID that has been in common use since 1976. Like other NSAIDs Naproxen provides analgesic, antipyretic and, in higher doses, anti-inflammatory effects. It is approved for the treatment of inflammatory rheumatic conditions, osteoarthritis, primary dysmenorrhea and musculoskeletal pain.

8 Specific objectives

8.1 Primary objective

To demonstrate that, in patients with sciatica, treatment with Naproxen 500 mg twice daily is superior to placebo for the improvement of leg pain intensity measured on a numeric rating scale (NRS) ranging from 0 to 10.

8.2 Secondary objectives

To demonstrate that, in patients with sciatica, treatment with Naproxen 500 mg twice daily is superior to placebo with respect to

- improvement in back pain intensity
- improvement in disability
- use of rescue medication
- global perceived change in sciatica/back problem
- improvement in sciatica symptom bothersomeness
- 30% and 50% improvement in leg pain
- concomitant use of opioid analgesics
- ability to work and study

STUDY METHODS

9 Trial Design

NIS is a multicenter, two-armed randomized, placebo controlled, double blind, parallel group, superiority phase IV trial.

10 Randomization

Study medicines will be packaged and labelled according to a pre-generated random number sequence; each sealed box will have a unique participant number. Computer-generated block randomization, stratified by center, will be used. Allocation to Naproxen or placebo will be at a 1:1 ratio.

11 Sample size

The sample size estimation is based on a minimum difference of interest between the Naproxen group and the placebo group of 1.5 at day 10. Assuming a standard deviation SD of 2.5 (see protocol for details and references), 90% power and a two-tailed 5% significance level, 60 subjects in each treatment arm is required. Allowing for a combined dropout and non-compliance rate $\leq 20\%$ a sample size of 150 was determined.

12 Framework

Analyses will be within a superiority hypothesis testing framework, comparing Naproxen to placebo.

13 Interim analyses and stopping guidance

13.1 Treatment analyses

No interim treatment analyses will be performed.

13.2 Early stopping

The safety profile of Naproxen is well documented and established, and the dosing is under its approved label use. There is no reason to expect Naproxen to affect the rate of serious sciatica complications such as lower extremity paresis or cauda equina syndrome. As Naproxen is used under its approved label use no interim safety analyses will be conducted.

14 Timing of final analysis

All outcomes will be analyzed jointly after the end of the trial, i.e. after the last visit of the last subject, and data locking.

15 Timing of outcome assessments

Primary outcome: Leg pain (the primary outcome) is measured daily from baseline (day 0) to end of treatment (day 10).

Secondary outcomes

- Back pain is measured like leg pain
- Disability, assessed by the Roland Morris Disability Questionnaire for Sciatica (RMDQ-S), is measured at day 0, 5 and 10
- Rescue medication consumption is measured (i) at the end-of study-visit (by pill count) and (ii) daily from day 1 to day 10 (by self-report).
- Global perceived change is measured at day 5 and 10.
- Sciatica bothersomeness, assessed by the Sciatica Bothersomeness Index (SBI), is measured at day 0, 5 and 10.
- Concomitant use of opioid analgesics is assessed on day 0, 5 and 12 (± 2).
- The ability to work or study is measured at day 0 and 10.

Table 1. Timing of outcome assessments

	Baseline	Start of treatment				End of treatment	End of study
–							

Day	0	1	2-4	5 (± 1)	6-9	10	12 (± 2)
	Visit	Home	Home	Home	Home	Home	Visit
-Leg pain -Back pain	X	X	X	X	X	X	X
-SBI -RMDQ-S	X			X		X	X
Global perceived change				X		X	X
Work/study	X					X	X
Rescue medication (pill count)							X
Rescue medication (self-report)		X	X	X	X	X	
Opiod use	X			X			X

SBI Sciatica Bothersomeness Index, RMDQ-S Roland Morris Disability Questionnaire for Sciatica.

Visit windows.

Patient reported outcomes are captured using a web based real-time electronic diary (ViedocMe). The questionnaires are available 24 hours on the scheduled date. The end of study visit is scheduled on day 12 (± 2).

STATISTICAL PRINCIPLES

16 Level of statistical significance

A two-tailed p value of less than 0.05 is considered to indicate statistical significance. We will report nominal p values.

17 Adjustment for multiplicity

We will not adjust for multiple comparisons. This trial has one primary outcome which will be analyzed in a single mixed-effect model and there are no planned subgroup analyses.

18 Confidence intervals

Parameter estimates will be reported with two-sided 95% confidence intervals (CI).

19 Adherence and protocol deviations

19.1 Adherence

The prescribed doses of study medication is one tablet twice daily for ten days, i.e. a total of 20 tablets. Adherence is assessed by the percentage of prescribed doses taken, measured by pill count if the bottle is returned. If the bottle is not

returned adherence will be based on self-report. Each day patients are asked to record study medication intake and give the reason if not taking the prescribed amount. Reasons for non-adherence will be reported based on patients' free-form text comments in the diaries, and investigators' comments in the case report forms (CRFs). This information will also be used in subsequent classification of potential missing data as being "missing not at random" (MNAR), "missing at random" (MAR) or "missing completely at random" (MCAR) [1].

19.2 *Protocol deviations*

Important (major) protocol deviations will be reported by the number of subjects who

- entered into the study not meeting the entry criteria
- developed withdrawal criteria during the study but were not withdrawn
- received the wrong study treatment or incorrect dose
- had less than 80% intervention adherence

Not important (minor) protocol deviations will be reported by the number of subjects who

- received drugs that they were encouraged to avoid during study, i.e. analgesics, NSAIDs, anti-depressants, tranquilizers, sleep medications, neuroleptics and anti-epileptic drugs, if not on a stable dose prior to enrollment.
- received drugs which would have excluded them from participating in the trial, i.e. anticoagulants, aspirin, serotonin reuptake inhibitors, systemic corticosteroids, diuretics, ACE-inhibitors and lithium.

20 Analysis populations

There will be 3 analysis populations:

1. The intention-to-treat (ITT) population, including all randomized subjects.
2. The per protocol (PP) population, including subjects without any important protocol deviations.
3. The safety population, including subjects who received at least one dose of study medication and who had at least one subsequent safety-related observation.

Amendment: Subjects who are withdrawn because they did not receive the study medication may be re-randomized. This requires that the reason for not receiving the study medication was unrelated to the subject's condition and that all eligibility criteria are met. In such cases the subject ID linked to the first randomization will be excluded from all analyses. The subject concerned will be analyzed according to the second randomization and included in the appropriate analysis populations.

TRIAL POPULATION

21 Screening data

The population of interest is patients with severe sciatica who are referred to the participating centers, i.e. outpatient pain/back clinics at public hospitals in Norway. To enhance recruitment primary care clinicians are invited to refer eligible patients. A prescreening log will be established including information about age, sex and whether the eligibility criteria were fulfilled. Reasons why eligible subjects were not enrolled will be noted.

22 Eligibility

See trial protocol for inclusion and exclusion criteria.

23 Recruitment

We will present a CONSORT [2] diagram comprising the number of participants who were screened, eligible, randomized, receiving their allocated treatment, withdrawn and lost to follow-up.

24 Withdrawal and loss to follow-up

Reasons for withdrawal from the study will be coded as follows:

- Voluntary discontinuation by the patient
- Safety reason as judged by the principal investigator
- Important (major) protocol deviations
- Incorrect enrolment i.e. the patient does not meet the required inclusion/exclusion criteria for the study
- Patient lost to follow-up
- A female patient becoming pregnant
- Patient's non-compliance to study treatment and/or procedures
- Death
- Other

Reasons for loss to follow-up will be provided if known. Depending on the data we will present the timing of withdrawal and loss to follow up in a Kaplan-Meier graph or incorporate it into the CONSORT flow diagram.

25 Baseline patient characteristics

Demographic and clinical characteristics will be summarised by assigned treatment group without comparisons, as shown in 32.1 (Planned table 1). Categorical variables will be summarised by frequencies and percentages. Percentages will be calculated according to the number of patients for whom data are available. Where values are missing, the denominator, which will be less than the number of patients assigned to the treatment group, will be reported either in the body or a footnote in the summary table. Continuous variables will be summarised by mean and standard deviation, or by medians and interquartile range (IQR).

ANALYSIS

26 Outcome definitions

26.1 Specification of outcomes.

The primary outcome is leg pain intensity (24 hours average), rated on a 0-10 NRS. Higher scores indicate more severe pain.

Secondary outcomes:

- Back pain intensity (24 hours average), rated on a 0-10 NRS.
- Disability, measured by RMDQ-S (0-23), higher scores indicate worse disability.
- Sciatica bothersomeness, measured by the SBI (0-24), higher scores indicate more symptom bothersomeness.
- $\geq 30\%$ improvement in leg pain score
- $\geq 50\%$ improvement in leg pain score
- Global perceived change measured on a 7-point Likert scale (sciatica/back problem completely gone, much better, better, a little better, no change, a little worse, worse and much worse).
- Rescue medication consumption, measured by pill count, i.e. the number of Paracetamol pills not returned at the end of study. If the Paracetamol package is not returned, self-report data from the electronic diary will be used. Higher rescue consumption indicates more pain.
- Concomitant use of opioids, higher consumption indicate more pain
- Ability to work or study full time, measured by 3 nominal categories (unable, able, other)

We consider the secondary outcomes to have equal importance.

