### 2.4 SECONDARY ENDPOINTS

- The change in back pain (24 hours average) rated on a 0-10 numeric rating scale (NRS) from baseline to day 10 based on longitudinal analyses of daily observations.
- The change in disability assessed by the Roland Morris Disability Questionnaire for sciatica (RMDQ-S) based on longitudinal analyses of observations at baseline, day 5 and day 10.
- The use of rescue medication, i.e. number of Paracetamol tablets taken between baseline and day 10.
- The number of patients who at day 5 and day 10 report their pain to be *completely gone, much better and better* on a Global Perceived Change (GPC) scale
- The change in sciatica symptoms assessed by the Sciatica Bothersomeness Index (SBI) based on longitudinal analyses of observations at baseline, day 5 and day 10.
- The number of patients who at day 5 and day 10 have a (i)  $\geq 30\%$  and a (ii)  $\geq 50\%$  reduction in leg pain score relative to baseline
- The use of (i) weak opioids and (ii) strong opioids assessed by the number of Defined Daily Doses (DDD) between baseline and day 10
- The number of patients who at day 10 are able to work/study as normal

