## **6 STUDY PROCEDURES**

### **6.1 FLOW CHART**

Table 1. Trial flow chart

	Baseline	Start of treatment			Halfway follow-up		End of treatment	Final study visit	Withdrawal
Day	0	1	2	3-4	5 ( $\pm 1$ )	6-9	10	12 ( $\pm 2$ )	within 7 days after withdrawal
	Visit	Home	Home	Home	Home/ Telephone	Home	Home	Visit	Visit
Informed consent	X								
Inclusion/exclusion	X								
Medical history (including previous use of NSAIDs for sciatica)	X								
Treatment of current sciatica episode	X								
Physical examination*	X								
Vital signs (blood pressure, pulse)	X							X	X
Questionnaires:									
Leg pain intensity, back pain intensity	X, X†	X	X	X	X	X	X	X	X
Questionnaires:									
SBI, RMDQ-S	X				X		X	X	X

	Baseline	Start of treatment			Halfway follow-up		End of treatment	Final study visit	Withdrawal
Day	0	1	2	3-4	5 ( $\pm 1$ )	6-9	10	12 ( $\pm 2$ )	within 7 days after withdrawal
Questionnaire: GPC					X		X	X	X
Questionnaire: Work/study	X						X	X	X
Patient's guess regarding correct treatment								X	X
Self-report of IMD and rescue medication intake		X	X	X	X	X	X		
Protocol compliance, patient discontinuation			X		X			X	
Adverse events, self-report		X	X	X	X	X	X		
Adverse events, investigator					X			X	X
Laboratory tests† (safety)	X							X	X
Pregnancy test (women of childbearing potential)	X								
Return of pill boxes								X	X

\*SLR, sensory, muscular strength and reflex status of the lower extremities

†On day 0 patients will record back and leg pain both at the clinic and at home in the evening

‡Haemoglobin, hematocrit, leucocytes, thrombocytes, creatinin/eGFR, ASAT, ALAT, ALP

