27.2 Analysis of secondary outcomes

- Back pain intensity will be analyzed using the same model used to analyze the primary outcome.
- Disability and sciatica bothersomeness will be analyzed using the same model used to analyze the primary outcome, but with 3 time points.
- Responder analyses, i.e. 30% and 50% improvement in leg pain intensity, will be performed using a mixed effects logistic regression model to obtain estimates of odds ratios (OR) and 95% CI. Based on the absolute risk reduction (ARR) between Naproxen and placebo we will calculate the numbers needed to treat (NNT) with 95% CI (NNT = 1/ARR).
- Rescue medication consumption and concomitant use of opioids during the treatment period will be analyzed using a suitable regression.
- Work/Study is an unordered categorical variable. The appropriate model is therefore a multinomial with repeated measurements and it will be analyzed using a GLMM.
- Global perceived change is an ordered categorical variable with repeated measurements and will be analyzed using a GLMM.

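### Rescue paracetamol is scored by a pill count at the day 12 (±2) visit although the endpoint ends at day 10, and the SAP and protocol disagree on when opioid use is recorded

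*SAP*

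**What the plan says.** **Rescue medication.** Protocol 2.4 defines the endpoint as the "number of Paracetamol tablets taken between baseline and day 10". SAP 27.2 has the same period in view: "Rescue medication consumption and concomitant use of opioids during the treatment period will be analyzed using a suitable regression". Protocol 5.4.2 sets that period at 10 days.

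The scoring rule in SAP 26.1 is different. Consumption is "measured by pill count, i.e. the number of Paracetamol pills not returned at the end of study". The fallback is: "If the Paracetamol package is not returned, self-report data from the electronic diary will be used". SAP 15 and its Table 1 place the pill count only at the last visit: "The end of study visit is scheduled on day 12", with a window of ±2 days. They schedule the rescue diary for days 1 to 10. The protocol flow chart agrees: its row "Self-report of IMD and rescue medication intake" is marked on days 1 to 10 and on no later day. Protocol 6.5.5 derives the count as tablets handed out at baseline minus tablets returned, with no cut-off at day 10. Protocol 6.2.5 lets a withdrawn patient return packs up to 7 days after withdrawal. Where diary and count disagree, protocol 5.8 prefers the count.

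**Opioids.** Protocol 2.4 measures weak and strong opioids alike, "assessed by the number of Defined Daily Doses (DDD) between baseline and day 10". Protocol 5.3 and 6.5.5 say other pain medication is recorded every day. SAP 15 lists opioid assessments on days 0, 5 and 12 (±2) only. SAP 26.2 needs a weak-opioid total from day 0 to day 10. For strong opioids it gives no window and changes the unit to morphine milligram equivalents (MME).

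**The concern.** The planned result is a between-group difference in tablets during treatment. Followed as written, SAP 26.1 measures a different period from the one the endpoint names, and a period that varies between patients. Days after day 10 are off study drug in both arms, so tablets taken then say nothing direct about the stated contrast. Because no rescue intake is recorded after day 10, the analyst cannot remove them afterwards.

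For opioids, the SAP's own weak-opioid score needs intake up to day 10, yet no opioid assessment in the SAP falls on day 10 unless the last visit happens to be that day. If dated daily intake exists, as the protocol says, the score can be computed. If only the SAP schedule was followed, it can only be approximated.

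At stake is the interpretation of the rescue and opioid results, which SAP 26.1 ranks as equal in importance to the other secondary outcomes.

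**Working it through.** The documents give no figure for the rescue or opioid outcomes to reproduce. The only sample-size figure concerns leg pain and plays no part here. It does reproduce: difference 1.5, SD 2.5, 90% power and two-sided 5% give 59.35 by the t-test, so 60 per arm, and 60 / (1 − 0.20) = 75 per arm, 150 in total.

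**Inputs.** Endpoint ends day 10 (protocol 2.4). Last visit on day 10 to 14 (SAP 15). Diary on days 1-10 (SAP 15, protocol flow chart). Stated ceiling of 6 tablets in 24 hours, used here only as an arithmetic bound, and a pack of 100 tablets (protocol 5.2.1). Return within 7 days after withdrawal (protocol 6.2.5).

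**1. Off-treatment share of the count, from day 1.** With return on day v, the share is (v − 10) / v and the excess at the ceiling is 6 × (v − 10).

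| Return day | Off-treatment days | Share of counted days | Excess at the ceiling |
|---|---|---|---|
| 10 | 0 | 0 of 10 (0%) | 0 |
| 11 | 1 | 1 of 11 (9%) | 6 |
| 12 (nominal) | 2 | 2 of 12 (17%) | 12 |
| 13 | 3 | 3 of 13 (23%) | 18 |
| 14 (latest) | 4 | 4 of 14 (29%) | 24 |

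The comparison value for days 1-10 is 6 × 10 = 60. The pack size does not limit the excess: day 0 to day 14 at the ceiling is 6 × 15 = 90, below 100.

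**2. Other count periods in the same variable.** Unreturned packs use the diary, so 10 days. A withdrawal on day w allows return from day w to day w + 7. Withdrawal on day 1 or 2 ends the count by day 8 or 9; withdrawal on day 9 can extend it to day 16.

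**3. Effect on the between-group difference.** Let k be off-treatment days, m the mean daily tablets after day 10, and p the share of packs returned in each arm. Assume the same return day for all, and that returning the pack is unrelated to use. Then:

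shift in (placebo − Naproxen) = k × (p_placebo × m_placebo − p_Naproxen × m_Naproxen).

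- All packs returned, equal use after day 10: shift 0.
- All packs returned, an assumed gap of 1 tablet a day either way: ±2 tablets at day 12, ±4 at day 14.
- Equal use of 2 to 4 tablets a day and return shares 10 percentage points apart (both assumed): 2 × 2 × 0.10 = 0.4 to 2 × 4 × 0.10 = 0.8 tablets at day 12; 0.8 to 1.6 at day 14.

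**4. Day 0.** The pack is given at baseline and study medication starts the next morning (protocol 6.2.2). The count therefore begins on day 0 and the diary on day 1. Protocol 2.4 counts from baseline, so day-0 tablets after dispensing can fairly be read as part of the endpoint. This is a mismatch between the two sources.

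**5. Opioids side by side.**

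| | Protocol | SAP |
|---|---|---|
| Recording | daily (5.3, 6.5.5) | days 0, 5 and 12 ±2 (15) |
| Window, weak | baseline to day 10 (2.4) | day 0 to day 10 (26.2) |
| Window, strong | baseline to day 10 (2.4) | not stated in 26.2; treatment period in 27.2 |
| Unit, strong | DDD (2.4) | MME (26.2) |

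The protocol flow chart has no row for other pain medication, so it does not settle the recording question.

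**The case against.** The strongest reply is that the pill count was chosen on purpose. Protocol 5.8 regards counts as generally more accurate than self-report and gives them priority, protocol 6.5.5 describes the count, and SAP 26.1 follows. Moving to the diary exchanges a window error for a reporting error, and the documents hold no data on which is larger. That stands as a real cost. It does not repair the window, because a count cannot be cut back to day 10 however accurate it is.

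A second reply is that the regression for this outcome is left open, so an offset for days from dispensing to return could absorb unequal lengths. It would, but it treats a day off study drug like a day on it. Asking about use after day 10 at the last visit would allow subtraction, but it needs a new data item and does not help for patients already finished.

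Third, allocation is randomised and blinded, nothing suggests that visit day differs by arm, and the 12 and 24 tablets are ceilings. All correct, and the conclusion is limited accordingly.

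A reader might also infer more than the documents support:

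- That the rule favours one arm. No intake or return rates are given, so no direction can be stated.
- That day-0 tablets are out of window. The protocol's wording arguably includes them.
- That daily opioid data do not exist. The two documents conflict, and only the e-CRF can show which was implemented.
- That SAP 27.3 contradicts itself by adjusting the opioid analyses for baseline pain instead of baseline opioid use. It states a general rule and then names a specific covariate, which reads as an intended exception.

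**Conclusion.** The point holds. The rescue outcome as defined in SAP 26.1 covers a period other than the one in protocol 2.4 and SAP 27.2, and not the same period for every patient. At the nominal visit 2 of 12 counted days are off treatment, and at the latest scheduled visit 4 of 14. The upper bound on the excess is 12 or 24 tablets per patient, which rests on the protocol's stated ceiling being reached every day. The shift in the treatment difference depends on use after day 10 and on return rates, neither of which the documents give. It may go either way and is zero if, for instance, all packs are returned on the same day and use after day 10 is equal in both arms.

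The opioid recording schedules conflict outright, and so do the units for strong opioids. The missing strong-opioid window in SAP 26.2 needs clarification only, since protocol 2.4 and SAP 27.2 imply it.

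Only secondary outcomes are affected. The changes should be made before unblinding, but they do not bear on the trial's main conclusion.

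**What to change.** **Rescue (SAP 26.1, before unblinding).** Use one window for all patients: diary-reported paracetamol tablets on days 1-10 as the main measure, with a statement that the diary does not cover day 0. Keep the pill count as a sensitivity analysis, with an offset for days from dispensing to return. Say whether missing diary days are imputed by day or on the total under SAP 28.3. Record in the SAP that this departs from the pill-count priority in protocol 5.8.

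**Opioids (SAP 15, 26.2).** Reconcile SAP 15 with protocol 5.3 and 6.5.5 against the e-CRF version listed in SAP 33.3. If dated daily intake does not exist, say that the total to day 10 is approximate. Use the same window, ending at day 10, for weak and strong opioids, and settle DDD or MME for strong opioids.

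**Optional (SAP 27.3).** Add baseline opioid use (yes/no, as tabulated in Planned Table 1) as a covariate in the opioid analyses. The outcome total should then start on day 1, so that day 0 is not both covariate and outcome.

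**Cost.** Mostly SAP wording and one check of the e-CRF, since the diary and the count are both already scheduled. The price is reliance on self-report: multiple imputation covers missing diary days but not misreported ones, which is what the pill-count sensitivity analysis is for. Changing protocol 5.8 itself would be an amendment needing approval under protocol 10.3; recording the departure in the SAP leaves the protocol text as it is.
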